## 4.2 DISCUSSION OF STUDY DESIGN

There will be no randomization of 1 to 5 year-olds in Cohort A of Stage I, as all subjects will receive two  $10^6$  CCID50 doses of the 2016 lot of candidate 2. In Cohort B of Stage I the first 50 subjects will receive the  $10^5$  CCID50 dose and subjects will be randomized to receive either one or two doses of the respective vaccine dosage. Only one candidate vaccine will be used in Stage I, so clinical staff will not be blinded to candidate.

In Stage II, for the assessment of both candidates prepared in 2018, randomization to candidate will be performed in both 1 to 5 year-old and infant cohorts to increase the likelihood that known and unknown subject attributes (e.g., demographic and baseline characteristics) are evenly balanced across candidate and one and two dose groups. Randomization of infants to 2018 lots in Stage II will be conducted within dose level (randomized to candidate and number of doses within low dose, then separate randomization to candidate and number of doses within high dose).

## **5. SELECTION OF STUDY POPULATION**

For details on the sample size calculation, please refer to Section 10.2.

### **5.1 INCLUSION CRITERIA**

1. For Cohort A children enrolled at 1 to 5 years of age who have previously been fully vaccinated according to MoH recommendations with OPV and/or IPV.
2. For Cohort B infants enrolled at 6 weeks of age (-1, + 2 weeks) with birth weight >2,500 gm. To be eligible to continue into the experimental phase of the study infants must be vaccinated with 3 doses of bOPV and one dose of IPV prior to administration of the study vaccine at 18–22 weeks of age to take into account the visit windows for enrollment (age 6 weeks, -1 or + 2 weeks) and subsequent OPV vaccination windows ( $\pm$  1 week). The last polio vaccine must have been administered at least 4 weeks prior to the first dose of study vaccine. Subjects in Cohort B who do not complete the three routine vaccination visits will be replaced in the study, and their parents/guardians will be encouraged to complete the primary vaccinations series.
3. Healthy children without obvious medical conditions like immunodeficiency diseases, severe congenital malformations, severe neurological diseases or any other disease that require high doses of corticosteroids or immunotherapies that preclude the subject to be in the study as established by the medical history and physical examination.
4. Written informed consent obtained from 1 or 2 parent(s) or legal guardian(s) as per country regulations.

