## **PROTOCOL HISTORY**

Protocol History FIDEC – M5 – ABMG			
Document	Issue Date	Amendment Type	Comments
Initial Clinical Study Protocol	21 June 2018 (v 1.0)	-	This document
Protocol amendment 1	5 October 2018 (v 2.0)	Study design	Extensive changes to study design to allow sequential testing of two nOPV2 candidates, 1 and 2.
Protocol amendment 2	4 March 2019 (v 3.0)	Study design	Extensive changes to study design to allow concomitant, randomized testing of nOPV2 candidates 1 and 2 produced in 2018 using final working virus seed.

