## **TIME AND EVENTS SCHEDULE – 1 TO 5 YEAR-OLD GROUPS.**

Assessments	Groups A1H2 and A2H2									Follow-up phone contact
	Visit	1	2	3	4	5	6	7	8	9
Time of Visit (days) Visit Window	D 0	D 7 (± 2 days)	D 14 (± 3 days)	D 21 (± 2 days)	D 28 (+ 2 days)	D 35 a (± 2 days)	D 42 a (± 3 days)	D 49 a (± 2 days)	D 56 a b (+ 2 days)	D 208 (± 14 days)
Informed consent c	X									
In-/exclusion criteria	X									
Medical history/concomitant diseases	X									
Medication/Vaccination history d	X									
Demographic data	X									
Physical examination	X	X			X				X	
Clinical laboratory tests e	X f	X			X f				X	
Administration of nOPV2 g,h	X				X					
Serum sample for polio antibodies	X f	X			X f				X	
Stool sample for viral culture/quantitative PCR, stool sample for potential poliovirus sequencing, stool sample for potential neurovirulence i	X i -----X		X	X	X-----X		X	X	X	
Solicited systemic AEs (Diary) j	X-----X				X-----X					
Remote contact for safety follow-up k	X-----X		X	X-----X			X		X	
Concomitant therapies	X	X	X	X	X	X	X	X	X	X
Adverse events l	X	X	X	X	X	X	X	X	X	X m

- Days 35, 42, 49 and 56 are defined in relation to Day 28 (7, 14, 21 and 28 days after the second dose, respectively).
- In case of early termination the subjects will be asked to return to the clinical site within 14 days after discontinuation for assessments as outlined on Day 56.
- No study-related assessment is to be carried out before signing the informed consent form, which can be obtained up to 4 weeks before Visit 1.
- Including polio vaccination history.
- For a list of assessments, please see Appendix 1: Overview of Laboratory Assessments. If an anomaly is found at 7 days post-dose 1, further investigations will be done at the investigator's medical judgement.
- Prior to vaccination.
- Group A1H2[2018] receives 10^6 CCID50 candidate 1 (2018), Group A2H2[2016] receives 10^6 CCID50 candidate 2 (2016), Group A2H2[2018] receives 10^6 CCID50 candidate 2 (2018).

CLINICAL STUDY PROTOCOL – M5

Amendment 2

4 March 2019 (Version 3.0)

- h. The subjects will be kept under medical supervision for at least 30 min after vaccination.

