## 1.2 OVERALL RATIONALE FOR THE STUDY

Sabin type 2 poliovirus was withdrawn from routine use globally from April 2016 as per the SAGE recommendations. Following this cessation of OPV2, stockpiles of mOPV2 are to be maintained for potential use if necessary in response to a future outbreak, but there will still be a risk of cVDPV2 from Sabin 2 in settings of low population immunity. Two nOPV2 vaccine candidates have been developed as attenuated serotype 2 polioviruses derived from a modified Sabin 2 infectious cDNA clone. nOPV2 Candidate 1 (*S2/cre5/S15domV/rec1/hifi3*) and nOPV2 Candidate 2 (*S2/S15domV/CpG40*) were generated by modifying the Sabin-2 RNA sequence to improve phenotypic stability and make the strains less prone to reversion to virulence. The two nOPV2 candidate vaccine strains have been used as an investigational medicinal product (IMP) in a first-in-human (FIH) Phase 1 containment trial (M4a) in two groups of 15 healthy IPV-only vaccinated adults in Belgium, to evaluate the general safety and immunogenicity of both of the nOPV2 candidate vaccine strains (EudraCT number 2017-000908-21, ClinicalTrials.gov: NCT03430349). In general, the two vaccine candidates were well tolerated with no serious adverse events reported, and no severe illnesses thought to be due to the vaccine candidates. Most health events reported during the study were generally mild, and all resolved.

Two participants (one with each nOPV2 vaccine candidate) exhibited transient, asymptomatic, severe elevations of aspartate aminotransferase (AST) associated with mild or moderate elevation of alanine aminotransferase (ALT) and severe elevation of creatine kinase (CK), but with no elevation of either gamma-glutamyltransferase (GGT) or bilirubin and with complete resolution to normal values. Other AEs on the basis of AST elevations were asymptomatic and generally mild and self-resolving, and also associated with elevated CK levels but normal GGT and bilirubin levels. All AEs on the basis of ALT elevations were transient and asymptomatic, with only one moderate AE

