**Further investigation is underway in adults** (study M4) from whom additional safety and immunogenicity data will be obtained. Although the long-term collection of safety data will still be ongoing at the time of enrolment for the present study in young children and infants, this study was only initiated when adequate safety follow-up of the M4 study in adults had been obtained according to the sponsor and DSMB. The present study is being performed to generate data in a similar fashion on the safety, immunogenicity (humoral and intestinal) and genetic stability endpoints of these novel nOPV2 candidates in children aged 1 to 5 years and in infants approximately 18 weeks of age vaccinated with bOPV-IPV. The overall development of nOPV2 was designed before the global cessation of OPV2 use which allowed studies to be started with mOPV2 before April 2016 with similar study design to this one (specifically M2) to provide historical control data against which to compare the novel nOPV2 candidates. This will allow comparison of data from this study with data that is already being generated on the immunogenicity, safety, and genetic stability of the mOPV2 vaccine in M2 in a comparable 18–22 week-old infant population (prevaccinated with bOPV and IPV). These comparisons will support the selection of which candidate to take further in development.

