- To assess the extent of viral shedding in stool at fixed time points following administration of one dose of the nOPV2 candidates (2016 and 2018 lots) at the  $10^6$  CCID50 dose level in healthy children aged 1 to 5 years, and in infants at approximately 18–22 weeks of age, and contrast this shedding with a control sample of participants receiving the same vaccination schedule followed by one dose of Sabin mOPV2 in a prior study (M2) designed to serve as a control for the current study.
- To assess the potential for neurovirulence of virus isolated from a subset of stool samples of children aged 1 to 5 years, and infants at approximately 18–22 weeks of age after having been previously vaccinated with 3 doses of bOPV and 1 dose of IPV, following one dose of the nOPV2 candidates (2018 lots) at the  $10^6$  CCID50 dose level, as measured in an animal model, and contrast this with a control sample of participants receiving the same vaccination schedule followed by one dose of Sabin mOPV2 in a prior study (M2) designed to serve as a control for the current study.

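### The Cohort A shedding and seroconversion contrasts with M2 take no account of prior type 2 OPV, although type 2 OPV was withdrawn between the start of M2 and M5

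*Combined protocol and SAP*

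**What the plan says.** **Eligibility.** Section 5.1 takes into Cohort A "children enrolled at 1 to 5 years of age who have previously been fully vaccinated according to MoH recommendations with OPV and/or IPV". Neither it nor the synopsis asks whether the earlier OPV contained type 2, or whether vaccination fell before or after the withdrawal.

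**Timing.** Section 1.2 states that "Sabin type 2 poliovirus was withdrawn from routine use globally from April 2016". The same section explains that the development plan "allowed studies to be started with mOPV2 before April 2016", M2 being the study meant. The M5 protocol is dated 21 June 2018 (version 1.0) to 4 March 2019 (version 3.0).

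**The contrast.** The shedding objective in section 2.2 covers 1 to 5 year-olds as well as infants, and sets out to "contrast this shedding with a control sample of participants receiving the same vaccination schedule followed by one dose of Sabin mOPV2". The neurovirulence objective uses the same description of the control. The Cohort A immunogenicity objective, which includes seroconversion, claims only a similar age. Section 10.1 shows M2 data beside M5 data as though both had been gathered at the same time. Section 10.1.2 says the Stage II interim document will formally compare primary and secondary endpoints, viral shedding among them, with M2. No stratum, covariate or subgroup for polio vaccine history is named.

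**Allocation.** Stage I Cohort A is a single non-randomised group. Stage II Cohort A is randomised 50:50 to candidate in permuted blocks (section 6.6), with no stratification factor named.

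**Data held.** The Cohort A schedule records medication and vaccination history, "Including polio vaccination history", and takes a Day 0 serum sample for polio antibodies. Section 5.2 asks for the number of earlier polio doses. Neither place asks for vaccine type or dates.

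**The concern.** The protocol itself ties shedding to prior immunity. Section 8.3 treats shedding as an indicator of intestinal immunity, and section 1.2.1 says excretion lasts longer in unprotected populations. If fewer M5 than M2 children had earlier OPV2, and if that exposure lowers shedding, nOPV2 would appear to shed more relative to mOPV2 than it really does. A true reduction could be hidden. The opposite imbalance would flatter nOPV2.

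The infants have a fixed bOPV-IPV schedule that makes M2 and M5 comparable on this point. Cohort A has none, so the same-schedule description is not secured for the older children.

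Two uses of the data give this weight. Section 1.2 says the M2 comparisons will support the choice of candidate. Section 10.1.5 requires at least 4.0 log10 CCID50 per gram before a stool can enter the mouse assay, and five or more such samples per cohort in both studies before a comparison with M2 is made. A shedding difference driven by history could change which Cohort A stools qualify, and whether there are enough of them.

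**Working it through.** **1. The plan's own figures.** Section 10.2 sizes Cohort A for safety. 1 − 0.95^45 = 0.9006, which meets the stated 90%, and 45 / 0.90 = 50 per group. For the infants, exact enumeration of the Miettinen-Nurminen test with 129 against 91 subjects, both rates 95%, margin 10% and one-sided 0.025 gives power 0.904 against the stated 90%; 129 / 0.80 = 161.25, so 162. All reproduce, and none depends on Cohort A vaccine history.

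**2. How many M5 children could have had OPV2 as infants.** Assumptions: uniform ages from 1 to a top age, first possible dose at 6 weeks (0.115 years), cut-off 1 April 2016.

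Share = (top age − (years since cut-off + 0.115)) / (top age − 1)

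- Enrolled 4 March 2019 (2.921 years): (5 − 3.036)/4 = 0.49, or (6 − 3.036)/5 = 0.59.
- Enrolled 5 October 2018: 0.59 to 0.67.
- Enrolled 1 October 2019: 0.35 to 0.48.

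These are ceilings. Being old enough is not the same as having received OPV2, and the share is 0 if all had only IPV and bOPV. The supportable range is therefore about 0 to 0.67.

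**3. Bias in the M5 minus M2 contrast.** Let the assumed effect be the reduction in shedding positivity from earlier OPV2, in percentage points.

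Bias = (share exposed in M2 − share exposed in M5) × effect

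| M2 exposed | M5 exposed | Effect 10 | Effect 20 | Effect 30 |
|---|---|---|---|---|
| 100% | 50% | 5 | 10 | 15 |
| 100% | 0% | 10 | 20 | 30 |
| 50% | 50% | 0 | 0 | 0 |
| 50% | 60% | −1 | −2 | −3 |

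A positive bias makes nOPV2 look worse than it is. Every share and effect in the table is an assumption; the documents supply none.

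**4. Candidate 1 against candidate 2 in Stage II.** With 100 children split 50:50 at random, the hypergeometric SD of the between-group difference in exposed share is 7.2 points at an overall share of 0.15, 9.2 at 0.30 and 10.1 at 0.50. The chance of a gap of 20 points or more is 0.4%, 4.9% and 7.1% respectively. This is random variation with mean zero.

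**The case against.** The strongest reply is that the documents permit a mix but do not show one. Section 1.2.1 describes local routine use as IPV, with a booster that lacks type 2, and gives no changeover date. M2 is said only to have started before April 2016; its children's histories and its end date are not given. If M2 children were also primed mainly with IPV, the gap could be small or nil. This stands, and it rules out any firm estimate. A reader might infer that Cohort A certainly mixes exposed and unexposed children, or that M2 was fully exposed; neither is documented. The household rule in section 5.2 accepts tOPV as an alternative to IPV for contacts aged 18 months to 10 years. So the protocol expects such histories locally, but it does not count them.

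A reader might also infer that unstratified allocation confounds the candidate comparison. It does not: randomisation leaves chance imbalance only, and no formal test of candidate 1 against candidate 2 is specified.

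Nor does history act directly on the mouse assay through the quantity shed. Section 8.4 dilutes amplified virus to a fixed inoculum, so the documents support an effect only through which samples qualify.

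Finally, shedding is secondary and called descriptive in section 3.2, and Cohort A is sized for safety. That lowers the priority. It does not remove the point, given the formal comparison promised in section 10.1.2.

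**Conclusion.** The point holds as a gap in the planned analysis. OPV2 withdrawal falls between the start of M2 and M5, Cohort A eligibility ignores it, and the M2 contrasts are unadjusted. Shedding and seroconversion in 1 to 5 year-olds can therefore be confounded by OPV2 history, and selection of Cohort A stools for neurovirulence testing can be affected. The size is unknown. The 5 to 15-point illustration requires full exposure in M2, half in M5 and an effect of 10 to 30 points.

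It would be too strong to say that vaccine and history cannot be separated. M5 collects polio history and a Day 0 titre; the plan simply does not use them for this purpose. How far separation is possible against M2 depends on M2 records that the documents do not describe. The primary infant comparison and its sample size are untouched.

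**What to change.** - In the Day 0 polio history, capture vaccine type (tOPV, bOPV, IPV) and dates. Obtain the same for M2 where held.
- Tabulate prior OPV2 exposure and Day 0 type 2 titre for each Cohort A group and for the M2 1 to 5 year-olds.
- Report Cohort A shedding and seroconversion, with their M2 contrasts, stratified by or adjusted for prior OPV2 exposure, beside the unadjusted result. If M2 histories are unavailable, use Day 0 type 2 titre. It is a partial substitute, since a serum titre may also reflect IPV.
- Show the OPV2 history of children contributing neurovirulence samples.
- In section 2.2, remove the same-schedule description of the control for the 1 to 5 year-olds.

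Stratifying the Stage II Cohort A randomisation is optional; it would remove only chance imbalance. The M2 contrast should not be restricted to an OPV2-experienced stratum unless M2 histories support it. If M2 children were not all exposed, that restriction would create a mismatch. It would also leave at most about 18 to 30 of 50 per group on the 2019 figures (0.35 × 50 = 17.5; 0.59 × 50 = 29.5).

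The cost is a few history fields, a request for M2 records, and some tables in the SAP, which section 10.1 leaves open until before database lock. The downside is small cells and wide intervals in a secondary analysis.

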### **5.2 EXCLUSION CRITERIA**

Subjects meeting any of the following criteria are excluded from participation in this study:

1. For all participants the presence of anyone under 10 years of age in the subject's household (living in the same house or apartment unit) who does not have complete "age appropriate" vaccination status with respect to poliovirus vaccines at the time of study vaccine administration. For household members younger than 18 months age appropriate vaccination is at least three (3) doses of IPV. For household members between 18 months and 10 years "age appropriate" vaccination is at least three (3) doses of IPV or tOPV plus one (1) booster dose of any antipolio vaccine.
2. For all participants having a member of the subject's household (living in the same house or apartment unit) who is under 6 months of age at the moment of study vaccine administration.
3. For all participants having a member of the subject's household (living in the same house or apartment unit) who has received OPV in the previous 3 months before study vaccine administration.

4. For Cohort A: receipt of polio vaccines within the 3 months prior to the administration of the study vaccine (number of previous polio vaccine doses to be documented). Any other vaccine 4 weeks before study entry.
5. For Cohort A: any participating children attending day care or pre-school during their participation in the study until one month after their last nOPV2 administration.
6. For Cohort B: any receipt of polio vaccines prior to administration of the study vaccine other than 3 doses of bOPV and 1 dose of IPV.
7. Any confirmed or suspected immunosuppressive or known immunodeficient condition including human immunodeficiency virus (HIV) infection in the potential participant or any member of the subject's household.
8. Family history of congenital or hereditary immunodeficiency.
9. Major congenital defects or serious uncontrolled chronic illness (neurologic, pulmonary, gastrointestinal, hepatic, renal, or endocrine).
10. Known allergy to any component of the study vaccines or to any antibiotics, that share molecular composition with the nOPV2 vaccines.
11. Uncontrolled coagulopathy or blood disorder contraindicating intramuscular injections (of IPV).
12. Administration of immunoglobulins and/or any blood products since birth or planned administration during the study period.
13. Acute severe febrile illness at day of vaccination deemed by the Investigator to be a contraindication for vaccination (the child can be included at a later time if within age window and all inclusion criteria are met.).
14. Subject who, in the opinion of the Investigator, is unlikely to comply with the protocol or is inappropriate to be included in the study for the safety or the benefit-risk ratio of the subject.

### **5.3 CRITERIA FOR ELIMINATION FROM THE PER-PROTOCOL POPULATION**

Subjects with clinically relevant deviations for hematology and chemistry parameters will be excluded from the per-protocol analysis population (see Section 10.1). These subjects will continue in the study for safety follow-up and intention to treat analysis but will not receive further vaccine doses.

Subjects that receive any other vaccine (with the exception of influenza) during the whole study period will be removed from the per-protocol population, but not the total vaccinated population. These subjects will only contribute safety data to the total vaccinated population prior to administration of the non-study vaccine, although they will still be followed for safety for the remaining study duration, with data presented in separate summaries. They will not receive further study vaccine doses

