**Secondary**

The following endpoints will be evaluated by time-point, group and overall:

Safety:

- Incidence of any SAEs, of any AEs grade 3, and of any IMEs as of the informed consent signature date and throughout the study period in all groups.  
(The following will be considered IMEs: medically significant events that do not meet any of

---

the SAE criteria, but may require medical or surgical consultation or intervention to prevent one of the other serious outcomes listed in the SAE definition).

- Incidence of any mild and moderate solicited AEs for 7 days after the first dose in all groups and for 7 days after the second dose in all groups **receiving two doses**.
- Incidence of any mild and moderate unsolicited AEs throughout the study period by causal association with study vaccines.
- Incidence and description of deviations from normal clinical laboratory assessments at Day 0 and 28 days after first dose of nOPV2 in all groups, Day 7 after the first dose of nOPV2 candidates in **one dose groups**, and at 28 days after the second dose in all groups receiving two doses.

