and the balance mild. Half of the participants exhibited asymptomatic severe elevations of CK, most often at the day 7 assessment, with resolution of values elevated in the first couple of weeks post-vaccination to normal or close to normal. A feasible explanation for these transient enzyme elevations could be intermittent, intense exercise by the participants, who were confined in the contained unit for 28 days but with exercise facilities provided.

Both candidates were immunogenic and elicited the desired protective responses against poliovirus. Shedding of virus in stools was more limited for vaccine candidate 2 compared with candidate 1, with some volunteers having more prolonged shedding than others, but none of the volunteers had any illness associated with this shedding. Data was also collected on the potential neurovirulence of virus shed in stools, which to date has not detected any meaningful increase in neurovirulence of either nOPV2 candidate relative to the vaccine itself. Sequencing has confirmed that there were no reverting mutations in the main site of attenuation which are analogous to the domain V A481G reversion in Sabin OPV2.

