### **8.5.2 *Clinical Laboratory Tests***

Blood samples of up to 6 mL in both Cohorts will be collected at the time points indicated in the Time and Events Schedules.

Standard laboratory tests as outlined in Appendix 1 will be performed by a local laboratory.

The Investigator must review the laboratory report, document this review, and record any change occurring during the study he/she considers to be clinically relevant in the source documents and in the AE section of the eCRF. Laboratory values outside the normal range will be flagged and their clinical relevance will be assessed by the Investigator. A copy of all laboratory reports must be filed in the subject's medical records.

Samples that remain after protocol-specific assessments have been performed may be used for further exploratory work on polio, including cryofreezing for future immunological studies. No human DNA or RNA analysis will be performed.

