#### **10.1.1 Study Populations**

The following populations will be considered for analysis:

- Total Vaccinated population, defined as all subjects who received at least one dose of study vaccine.
- Per-Protocol (PP) population, consisting of all eligible study participants who are in the Total Vaccinated population and who receive all of the immunizations scheduled for the group to which they are allocated and excludes those subjects who received any therapy that could significantly affect the subject's immune status and those subjects who meet criteria outlined in Section 5.3. The per-protocol population will be adapted by time point to allow subjects to contribute data to per-protocol analyses until such time as they become disqualified. All deviations and violations occurring in the study will be reviewed prior to database lock and classified as either minor or major.

Unless specified otherwise, the Total Vaccinated population will be used for safety/tolerability analysis and analysis of demographics. Immunogenicity and viral shedding analyses will be primarily conducted in the per-protocol population.

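### Section 5.3 lets a post-dose laboratory deviation, most clearly one found at Day 7, remove an infant's Day 28 titre from the primary non-inferiority test

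*Combined protocol and SAP*

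**What the plan says.** Section 5.3 gives the rule: "Subjects with clinically relevant deviations for hematology and chemistry parameters will be excluded from the per-protocol analysis population". It continues: "These subjects will continue in the study for safety follow-up and intention to treat analysis but will not receive further vaccine doses". No time limit is given, and the mention of further doses shows that the rule reaches subjects who have already been vaccinated.

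Section 10.1.1 carries the rule into the per-protocol definition, which leaves out "those subjects who meet criteria outlined in Section 5.3", and then says "Immunogenicity and viral shedding analyses will be primarily conducted in the per-protocol population". The same section adapts the population by time point to "allow subjects to contribute data to per-protocol analyses until such time as they become disqualified". It defines two populations, Total Vaccinated and per-protocol; the intention-to-treat analysis named in 5.3 is not defined there.

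On testing, the Synopsis secondary endpoints list "Incidence and description of deviations from normal clinical laboratory assessments at Day 0 and 28 days after first dose of nOPV2 in all groups", with Day 7 added for the one-dose groups. Section 3.2 gives Day 7 for all groups. The one-dose infant schedule has a Day 7 laboratory test; the two-dose infant schedule has none. Section 8.5.2 says who judges: "Laboratory values outside the normal range will be flagged and their clinical relevance will be assessed by the Investigator". Section 5.3 sets no numerical threshold.

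Section 2.1 includes clinically relevant laboratory deviations in the co-primary safety objective. Section 10.2 sizes the primary comparison in per-protocol infants: 129 per candidate and dose level, against 91 per-protocol infants from M2.

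**The concern.** A per-protocol set should drop subjects for reasons that make the measurement uninterpretable. Here a subject can be dropped for something that happens after the vaccine is given and that the protocol itself treats as a possible vaccine effect. One co-primary outcome then helps to select the sample for the other.

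Three features make this harder to dismiss:

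- **Judgement.** The trigger is the investigator's view of clinical relevance, with no threshold in 5.3.
- **Uneven exposure.** By the schedules, 112 of the 162 infants in each candidate and dose-level group have a Day 7 test and 50 do not, yet all are pooled at Day 28.
- **Historical control.** Randomization cannot balance the filter against M2, and the documents do not say whether the 91 M2 infants were filtered in the same way.

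At stake is the only analysis set that the plan specifies for the non-inferiority claim. If excluded infants respond less well than the rest, the per-protocol rate overstates the vaccine; if they respond better, it understates it. The documents give no reason why a haematology or chemistry value should invalidate a neutralizing titre, and therapies affecting immune status are already a separate ground for exclusion in 10.1.1.

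**Working it through.** **1. Which deviations can reach the Day 28 endpoint.** Combining 5.3 with the time-point rule in 10.1.1:

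| Laboratory test | Infants tested | Effect on the Day 28 titre |
|---|---|---|
| Day 0 (pre-dose) | all | excluded, but not a vaccine effect |
| Day 7 | one-dose (two-dose: Synopsis and schedule say no, section 3.2 says yes) | excluded |
| Day 28 | all | not settled: laboratory sample and titre come from the same visit |
| Day 56 | two-dose | none; disqualification comes later |

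**2. The plan's own figures.** Inputs from section 10.2: 129 versus 91, 95% seroprotection on both sides, margin 10 points, one-sided alpha 0.025. Exact binomial enumeration of the Miettinen-Nurminen lower bound gives 90.4% power (stated 90%). Enrolment is 129 / 0.80 = 161.25, so 162 (stated 162). Both reproduce; the point is about selection, not arithmetic.

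**3. Shift in the observed rate.** Let f be the fraction excluded and s the seroprotection rate among them. The documents give neither, so both are assumptions. With an all-vaccinated rate of 95%, the per-protocol rate is (0.95 - f·s) / (1 - f):

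- f = 5%, s = 80%: (0.95 - 0.04) / 0.95 = 95.8%, a shift of +0.8 points
- f = 10%, s = 80%: (0.95 - 0.08) / 0.90 = 96.7%, a shift of +1.7 points
- f = 10%, s = 100%: (0.95 - 0.10) / 0.90 = 94.4%, a shift of -0.6 points

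**4. False non-inferiority.** Take a true all-vaccinated rate of 85% against 95%, exactly at the margin. The per-protocol rate is (0.85 - f·s) / (1 - f). The last column is the exact chance of declaring non-inferiority, with 129 and 91 analysed.

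| f | s | Per-protocol rate | Chance |
|---|---|---|---|
| none, or any f | 85% | 85.0% | 2.1% |
| 5% | 80% | 85.3% | 2.5% |
| 10% | 80% | 85.6% | 3.0% |
| 2% | 50% | 85.7% | 3.2% |
| 10% | 70% | 86.7% | 5.4% |
| 5% | 50% | 86.8% | 6.0% |
| 10% | 50% | 88.9% | 16.2% |

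The nominal level is 2.5%.

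**5. Power.** The 129 already allows for 20% loss: 162 × 0.80 = 129.6. Exact power is 86.1% at 116 and 83.5% at 103, but those sizes mean losing 1 - 116/162 = 28% and 1 - 103/162 = 36% of enrolled infants. Exact power is also saw-toothed (88.1% at 128, 89.4% at 122), so small differences should not be read closely.

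**The case against.** The strongest reply is that the time-point rule already protects the primary endpoint. It does so for Day 56 deviations and arguably for those found at Day 28. It does not help an infant disqualified at Day 7, three weeks before the titre that counts.

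It can also be said that the no-further-doses wording fits Cohort A better, since those children have a Day 7 test and a second dose and lie outside the primary immunogenicity endpoint. That is a fair reading of intent. But section 5.3 is not limited to Cohort A, and 10.1.1 applies it to everyone.

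A reader might infer from the adult study that many infants would be excluded: "Half of the participants exhibited asymptomatic severe elevations of CK, most often at the day 7 assessment". The documents do not support that step. Those elevations were asymptomatic, occurred in 30 confined adults with exercise facilities, and are attributed in 1.2 and 1.2.1 to likely exercise. The rule needs clinical relevance, not a severe grade alone. The adult data make exclusions conceivable but give no rate for infants.

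Two other stronger readings also fail. One is that comparability with M2 is broken: M2's rule is simply not stated. The other is that each exclusion costs power below 90%: the 20% allowance must be used up first.

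Finally, 10.1.1 says only that per-protocol is primary, and section 10.1 defers detail to an SAP finalized before database lock. A supportive analysis could still be added there; none is specified in the text available.

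**Conclusion.** The concern holds as a structural fault: as written, a Day 7 laboratory deviation removes a Day 28 titre from the primary test, and a Day 28 deviation may do so. No bias is shown. Its direction and size depend on how many infants are excluded and how they respond, and the documents give neither.

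At 5-10% excluded with 80% of them protected, the effect is small against a 10-point margin. The false non-inferiority rate passes well beyond its nominal level only if excluded infants respond much worse than the rest. If they respond alike, there is no distortion.

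The unequal Day 7 exposure rests on the infant schedules and the Synopsis; section 3.2 says otherwise, and the passages must be reconciled.

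**What to change.** Before the Stage II database freeze:

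- State in 5.3 and 10.1.1 that post-dose laboratory deviations, at Day 7 or Day 28, do not remove a Day 28 titre from the primary per-protocol immunogenicity analysis. Leave the rule on further doses as it is.
- Replace the undefined intention-to-treat analysis with a pre-specified supportive run of the same -10% Miettinen-Nurminen comparison in Total Vaccinated infants with a Day 28 titre. It should not be an added success criterion.
- Report laboratory-based exclusions by group and time point.
- Apply the same per-protocol rule to the M2 infants where the M2 data allow, and say so where they do not.
- Reconcile the Synopsis, section 3.2 and the two-dose infant schedule on Day 7 laboratory testing.

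The cost is a few sentences of protocol and SAP wording and one extra table. Keeping these titres needs no additional subjects or samples.
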